## 4. INVESTIGATIONAL PLAN

### 4.1 Overall Study Design

The Carolinas Cardiogenic Shock Initiative is a clinical pathway and process improvement protocol already agreed upon by participating sites, to improve care by using a standardized algorithm to treat patients with AMI and CS. This prospective registry will capture data from this protocol as a multi-site research project in parallel with this standardized non-research clinic workflow protocol. Participating providers will follow the clinical protocol as standard of care for AMICS patients, as clinically appropriate. Patients who have been admitted and diagnosed with AMICS and meet all eligibility criteria will have their data entered in this registry.

All eligible patients will be entered into the registry and follow-up via the EMR and/or SSDI will occur at 30 days and one year to assess mortality. No additional provider appointments or further testing will be required as a part of this Registry, other than what each provider feels is medically necessary and indicated as a part of the patients' care plan.

Treatment decisions and timing will follow an approved clinical protocol and algorithm (see Appendix A) based on shock severity classification. The research team at each site will capture data generated during standard of care lab tests and clinical procedures, as well as data collected during clinical visits from eligible patients. Our target accrual is approximately 672 patients, cumulative across all participating sites.

Many of the patient specific outcomes and variables of interest for this study, are already submitted to the National Cardiovascular Data Registry (NCDR). Some additional data elements, as described in Appendix C, will also be captured. There are no benefits in participation other than the scientific knowledge gained, and the only alternative to participation is not participating.

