**Confidential**

The information provided in this document is strictly confidential and is intended solely for the guidance of the clinical investigation. Reproduction or disclosure of this document whether in part or in full to parties not associated with the clinical investigation, or its use for any other purpose, without the prior written consent of the Principal Investigator is not permitted.

Throughout this document, symbols indicating proprietary names (®, TM) are not displayed. Hence, the appearance of product names without these symbols does not imply that these names are not protected.

*Version 2 / Date 05/08/2020*

PROTOCOL SUMMARY	
Study Title	Carolinas Cardiogenic Shock Initiative
Study Design	This is a case series and prospective patient registry
Study Objectives	To determine if deferred or delayed implantation of Impella device based on shock severity index is non-inferior with respect to 1 month and 1 year mortality compared to standard clinical protocols that do not differentiate based on shock severity in adult patients following an initial diagnosis of acute myocardial infarction complicated by cardiogenic shock (AMICS).
Study Population	The registry will include all eligible subjects from approximately 5/1/2019 until 4/30/2024, at participating sites.
Study Procedures	Adult patients with a diagnosis of AMICS will have their clinically available data contribute to the project registry. Patients who meet criteria for inclusion into the registry will have their chart reviewed periodically for the purposes of the registry, for proof of survival at one month and one year post-admission. Social Security Death Index (SSDI) data will be used to determine mortality at one month and one year if unable to confirm using the electronic health record. Patient clinical data will be pulled from the medical record and entered or migrated into a database for comparison and analysis. All data collected for the study will originate in the medical record from clinically available information, from a national death database, or from other publically available data sources.

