
### *Power*

With respect to the 30-day primary end point of death, we estimated that an overall sample size of 672 patients would provide 80% power (at a one-sided alpha level of 0.025) to show the noninferiority of a standardized clinical protocol that selects patients for MCS based on shock severity to a standard clinical protocol that does not differentiate based on shock severity assuming the proportion of subjects observed with the event (death) during the study is 39.7% for the control group and 41.3% for the treatment group (Thiele et al., 2005; Thiele et al., 2013). The power was computed for the case when the actual treatment group proportion is 31%. The test statistic used is the one-sided Z test (unpooled).

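### The 80% power for Hypothesis 1 assumes a two-group total of 672, but the protocol describes 672 registry patients at sites that follow one algorithm and designates no standard-protocol control group

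*Protocol*

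**What the plan says.** Section 1.1 and section 4.4.2 set up Hypothesis 1 as a non-inferiority comparison on mortality between a protocol that selects patients for mechanical support by shock severity and standard protocols that do not.

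The Power paragraph of 4.4.2.1 treats this as a comparison of two groups. It states that "an overall sample size of 672 patients would provide 80% power", with assumed death rates of "39.7% for the control group and 41.3% for the treatment group". It adds: "The power was computed for the case when the actual treatment group proportion is 31" (per cent). The test is a one-sided unpooled Z test at alpha 0.025. No allocation ratio is given.

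The design text describes one stream of patients. The Protocol Summary says "This is a case series and prospective patient registry" and "The registry will include all eligible subjects from approximately 5/1/2019 until 4/30/2024, at participating sites". Section 4.1 describes the initiative as a "clinical pathway and process improvement protocol already agreed upon by participating sites" and says "Participating providers will follow the clinical protocol as standard of care for AMICS patients, as clinically appropriate". It then gives the accrual: "Our target accrual is approximately 672 patients, cumulative across all participating sites".

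**The concern.** The same 672 serves as the total for two groups in the power calculation and as the full intake of a registry whose sites treat by one algorithm. A test of the severity-based protocol against a standard one needs patients treated the standard way, and the protocol shown does not designate any.

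Hypothesis 1 is the only hypothesis with a power calculation, and that calculation is for the primary outcome, 30-day death. If the comparator is not fixed, a benchmark could be chosen after the registry's mortality is known. The non-inferiority conclusion would then depend on that choice and on the benchmark's case mix. The 80% would also be quoted for a comparison whose group sizes nobody has stated.

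**Working it through.** **Inputs** (Protocol 4.4.2.1, Power): control death rate 0.397; treatment-group figure 0.413, read as the non-inferiority limit; true treatment rate 0.31; one-sided alpha 0.025 (z = 1.96); power 80% (z = 0.8416); unpooled variance. The 1:1 split is not stated. It is inferred because it reproduces the protocol's total.

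**Step 1: reproduce 672.**

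n per group = (1.96 + 0.8416)² × (0.31 × 0.69 + 0.397 × 0.603) / (0.413 − 0.31)²

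= 7.849 × (0.2139 + 0.2394) / 0.01061 = 335.4, rounded up to 336.

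The total is 672, with power 80.07% at 336 + 336 (79.96% at 335 + 335). Had 672 been the size of each group, power would be 97.8%. The protocol's arithmetic is therefore right, and it is the arithmetic of a two-group total.

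**Step 2: power when controls are a minority within the 672.**

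Power = Φ(0.103 / √(0.2394/n_c + 0.2139/n_t) − 1.96), where n_c is the number of controls and n_t the number of algorithm patients. The control numbers are assumptions, since the protocol gives none.

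| Controls | Algorithm patients | Standard error | Power |
|---|---|---|---|
| 336 | 336 | 0.0367 | 80% |
| 168 | 504 | 0.0430 | 67% |
| 134 | 538 | 0.0467 | 60% |
| 67 | 605 | 0.0627 | 38% |

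**Step 3: all 672 are algorithm patients and controls are additional.** With n_t = 672, 231 controls give 79.91% and 232 give 80.04%. About 232 separate controls are needed, before any allowance for adjustment.

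**Step 4: all 672 are algorithm patients and there is no control group.** The term 0.2394/n_c has no value, so the two-sample power is undefined. What the registry can then deliver is an estimate. At 31% mortality the 95% half-width is 1.96 × √(0.31 × 0.69 / 672) = 0.035, or 3.5 percentage points.

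**Step 5: look for the comparator in the text.**
- Section 3 (Rationale) names the National Cardiogenic Shock Initiative protocol as a strategy that this initiative might improve on. It gives no cohort, period or number.
- The Power paragraph takes its event rates from published studies. It does not make the patients of those studies the control group.
- Section 4.1 mentions the national cardiovascular registry only as a place to which variables are already submitted. The Protocol Summary mentions public data only as a source of data.
- The coding of clinical protocol as typical or severity-based in the Approach paragraph of 4.4.2.1 is an example of how to read a hazard odds ratio. It assumes that both groups exist but does not supply them.

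**The case against.** The two statements of 672 do not clash as numbers. Both are totals, and one registry could hold both groups. This stands, so it would go too far to infer that the protocol gives 672 two incompatible meanings. The difficulty is that section 4.1 describes care under one algorithm and the protocol neither designates the other group nor gives the split.

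A reader might take patients managed off the algorithm as the controls, since 4.1 leaves room for clinical judgement. The protocol does not designate them. Such a comparison would be confounded by indication, and where the algorithm is standard of care these patients are unlikely to number 336.

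The comparator strategy is not wholly unknown. The Rationale names one, and the Power paragraph gives a control rate. This also stands and narrows the gap to the patients themselves: their source, period and number.

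The contents of Appendices A and C, the manual of procedures and any SAP are not at hand, and an external cohort could be specified there. The protocol describes Appendix A as an algorithm and Appendix C as data elements, neither of which would name a control group. A SAP can add analysis detail, but whether the 672 includes controls is a design matter on which 4.1 and 4.4.2.1 should agree.

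Finally, this is a registry with a broader primary objective (1.2). That limits the reach of the point, but 1.1 still states a non-inferiority hypothesis and 4.4.2.1 gives a decision rule for it.

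**Conclusion.** The point holds and should be settled before Hypothesis 1 is tested. The 672 and the 80% are correct for two groups of 336, but the registry as written has no designated control group, so the 80% is not a property of this design. On the protocol's own inputs, power is 80% only if half of the 672 are controls. It is 67% with 168 controls and 38% with 67, and it is undefined with none. If all 672 are algorithm patients, about 232 further controls would be needed.

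These figures rest on 41.3% being the limit, on the inferred equal split in the protocol's calculation, and on the protocol's rates of 39.7% and 31%.

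A reader might infer that the sample size is miscalculated or that the whole study lacks a valid analysis. The protocol supports neither: 672 reproduces exactly, and Hypothesis 2 and the primary objective in 1.2 do not depend on this comparison.

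**What to change.** Amend 4.1 and 4.4.2.1 to say whether the 672 includes standard-protocol controls, and withdraw the 80% or restate it for the actual group sizes. Then take one of two routes.

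- **If a control cohort is already available:** name it, starting from the strategy identified in the Rationale. Give its source, period and number separately from the algorithm patients, before outcomes are examined. Apply the eligibility criteria of 4.2.1 and 4.2.2 to it and adjust for baseline shock severity.
- **Otherwise:** report 30-day mortality as a single cohort with its 95% confidence interval, and drop the claim of non-inferiority to a standard protocol.

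No control number should be written in until a separate matter is reconciled: the Approach paragraph of 4.4.2.1 sets the margin as a ratio of 1.2, while the Power paragraph implies a limit of 41.3%. Under the protocol's discrete-time definition of hazard, and taking 39.7% as the 30-day hazard, a hazard ratio of 1.2 gives a limit of 1.2 × 39.7% = 47.6%. About 75 controls against 672 would then give 80% power, instead of 232.

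Either route costs a protocol amendment. The first also needs control records to be abstracted, and it is not known whether eligibility and shock severity can be recovered from them. The second costs no further data but gives a weaker conclusion, and any comparison that readers draw with outside figures remains exposed to case mix.

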#### 4.1.1 Primary Outcome Variable

The primary outcome variable will be 30-day all cause mortality.

#### 4.1.2 Secondary Outcome Variable(s)

Key secondary outcome variables for analysis may include but are not limited to:

- One year mortality
- length of ICU care
- requirement for renal replacement therapy
- dose and duration of catecholamine therapy

- requirement for implantation of an active LVAD or referral for cardiac transplantation
- time to support (arrival to tertiary facility to implantation)
- use of right heart catheterization
- Attainment of TIMI III flow post reperfusion
- Attainment of Cardiac power > 0.6 watts after completion of therapy
- Reduction or elimination of vasopressors and inotropic agents.
- blood products during admission
- hemolysis requiring device discontinuation
- vascular complication requiring surgery

## 4.2 Subject Selection

We have no reason to assume the patients who present with AMICS, will not be representative of the demographics of the region in which the participating site(s) are located. For this reason, we will not prioritize enrollment or recruitment based on demographics. Patients who present to the cardiac catheterization lab with AMICS at participating sites, and who meet inclusion criteria, will be included in the registry upon discharge. Data will be gathered in the usual manner for clinical purposes, for patients who die during their admission. The duration of the patient's enrollment in the registry is anticipated to last 1 year from AMICS. Recording of data in the registry is anticipated to last approximately five years.

### 4.2.1 Inclusion Criteria

**Subjects must meet all the following criteria:**

- Symptoms of acute myocardial infarction (AMI) with ECG and/or biomarker evidence of S-T elevation myocardial infarction (STEMI) or non-S-T elevation myocardial infarction (NSTEMI)
- Systolic blood pressure < 90mm at baseline or use of inotropes or vasopressors to maintain SBP > 90
- Evidence of end organ hypoperfusion
- Patient undergoes PCI

### 4.2.2 Exclusion Criteria

**Subjects must not meet any of the following criteria:**

- Evidence of Anoxic Brain Injury

- Unwitnessed out of hospital cardiac arrest or any cardiac arrest in which return of spontaneous circulation (ROSC) is not achieved in 30 minutes
- IABP placed prior to Impella
- Patient is already supported with an Impella
- Septic, anaphylactic, hemorrhagic, and neurologic causes of shock
- Non-ischemic causes of shock/hypotension (pulmonary embolism, pneumothorax, myocarditis, tamponade, etc.)
- Active bleeding for which mechanical circulatory support is contraindicated
- Recent major surgery for which mechanical circulatory support is contraindicated
- Mechanical complications of AMI (acute ventricular septal defect (VSD) or acute papillary muscle rupture)
- Known left ventricular thrombus for which mechanical circulatory support is contraindicated
- Mechanical aortic prosthetic valve
- Contraindication to intravenous systemic anticoagulation
- Receipt of thrombolytics with this event

### 4.3 Study Procedures

All inpatient data on eligible patients will come from the hospital inpatient records. Once the patient is deemed eligible, their clinical data will be entered or migrated into the research registry. Additional data will be collected at approximately one month and one year following AMICS, using the EMR and the SSDI.

The following are some of the variables which will be collected and recorded within the registry:

- Demographics
- Medical history
- Admission characteristics
- Diagnostic values
- Procedure dates and times
- Procedure characteristics
- Post-procedure information
- Discharge survival
- Survival at 1 month from AMICS
- Survival at 12 months from AMICS
- Additional Quality Metrics

### 4.4 Statistical Analysis

**4.4.1. Exploratory analysis.** Variable distributions will be examined using summary measures, tables, and graphics, such as histograms and scatter plots, where appropriate. Variables will initially be used as they were obtained; however, transformation may be

necessary or prove more informative. For example, continuous variables may be categorized, using common category boundaries found in the literature or based on percentiles of the variable distribution, in order to stratify the data. Student's t-test or the Wilcoxon rank-sum and chi-square statistics will be used to examine simple associations. For event history outcomes, we will primarily rely on survival analysis (i.e., event history modeling) to investigate if and when the event has occurred (Singer & Willett, 1993). For this study, the time scale for mortality will be recorded in discrete time intervals (i.e., baseline, one month, one year); therefore, the underlying continuous time-to-event process will be modeled using discrete time.

A major consideration will be the nested organization of the data. Patients (level-1) are nested within sites (level-2). When hierarchical data are analyzed without regard to the interdependence of the data type-I error rates are inflated (aggregation) or deflated (disaggregation) resulting in incorrect significance tests and invalid conclusions (Hox, 2002). While multilevel modeling methods explicitly account for the nested structure of data, this approach is not feasible because we do not have sufficient number of sites to treat these effects as random (Hox & Roberts, 2010; Roberts, Monaco, Stovall, & Foster, 2011). Therefore, each site will be evaluated for differences in multiple group analyses. If the site differences are trivial, we will collapse the data across sites (Little, 2013). Non-trivial differences will require a grouping variable for site in subsequent analyses.

**4.4.2. Analytic strategy.** Insights gained from the exploratory data analysis will then be used to fit appropriate statistical models to the data. Within the context of survival analyses, we will begin by modeling the unconditional model (no covariates) in order to establish a baseline model. Next, we will add covariates with time-varying (nonproportional hazard odds) effects. Using model constraints, we will then fit a proportional hazard odds model and compare. Finally, we will probe for hypothesized effects.

Specifically, our goal is, first, to examine the degree to which a standardized clinical protocol that selects patients for MCS based on shock severity will be non-inferior with respect to mortality when compared with a standard clinical protocol that does not differentiate based on shock severity among adult patients following an initial diagnosis of AMICS. Second, our goal is to determine the degree to which mortality rates of patients with AMICS differ on MCS exposure.

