#### Missing Data

Censoring will be assumed to be noninformative (i.e., the distribution of censoring times is independent of event times, conditional on the set of observed covariates). Missing data will be described in detail, including comparisons among participants that remained in the study to those that dropped out across demographic and outcome variables using t-tests, Little's MCAR test, or logistic regression (Nicholson, Deboeck, & Howard, 2015). Sensitivity analyses will be used to gauge the stability of inferences (Enders, 2010). When possible, we will use full-information maximum likelihood (FIML) estimation under the MAR missing data assumption (corresponding to the assumption of noninformative right

censoring) estimation option in the Mplus 7.3 software program to deal with missing data related to censoring and time-varying covariates with measurement intervals that do not correspond to the precision with which event times are measured. When appropriate, the robust standard error option, and the corresponding Satorra-Bentler correction for chi-square difference tests to evaluate site-level difference, will be used to correct for non-normality (Muthén & Masyn, 2005; Singer & Willett, 2003; Wang & Wang, 2012).

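### Site is dropped from the Hypothesis 1 model when a preliminary check finds site differences trivial, which can leave site confounding in the estimate if protocol use varies by site

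*Protocol*

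**What the plan says.** Section 4.4.1 notes that patients are nested within sites and that ignoring this distorts type I error, "resulting in incorrect significance tests and invalid conclusions". It rejects multilevel models because "we do not have sufficient number of sites to treat these effects as random". Sites are instead to be compared in multiple-group analyses, followed by a two-way rule: "If the site differences are trivial, we will collapse the data across sites", whereas "Non-trivial differences will require a grouping variable for site in subsequent analyses".

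The protocol does not define trivial. The Missing Data section mentions a "Satorra-Bentler correction for chi-square difference tests to evaluate site-level difference", without a significance level. The Hypothesis 1 model in section 4.4.2.1 has general time-invariant and time-varying covariates but names no site term. Non-inferiority is judged against a ratio of 1.2. The Power section states that "an overall sample size of 672 patients would provide 80% power", "at a one-sided alpha level of 0.025".

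**The concern.** The summary describes a case series and prospective registry, so nothing balances the two protocol groups within site. Whether site needs adjustment depends on its relation to both mortality and protocol group. A check of site differences in mortality covers only the first relation, and failing to find a difference does not show that none exists.

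Two consequences follow. A missed difference can bias the pooled estimate. The confidence interval compared with 1.2 also takes no account of the data having chosen the model. In a non-inferiority comparison, bias in favour of the new protocol leads directly to a false claim.

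**Working it through.** **1. The plan's own figure.** Inputs from the Power section: 39.7% (control), 41.3% (limit), 31% (true rate under the new protocol), one-sided 0.025, 80% power, unpooled Z. Equal allocation is assumed.

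n per group = (1.960 + 0.842)² × (0.397×0.603 + 0.31×0.69) / (0.413 − 0.31)² = 7.849 × 0.4533 / 0.010609 = 335.4, so 336 per group and 672 in total. The figure reproduces. The formula has no site term, so the fix does not change it.

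**2. Assumptions for the site question.** None of these is in the protocol: five sites of 134 (670 patients); 30-day mortality of 34, 37, 40, 43 and 46%; a site check at 0.05; a true odds ratio (new against standard protocol) of 1.2; non-inferiority declared if the upper 95% limit is below 1.2.

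**3. Power of the site check.** The squared deviations from 40% sum to 0.0036 + 0.0009 + 0 + 0.0009 + 0.0036 = 0.0090. The non-centrality is 134 × 0.0090 / (0.40 × 0.60) = 5.03. On 4 degrees of freedom (critical value 9.49) the power is 39.8%.

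**4. Bias from pooling, shares 70, 60, 50, 40, 30% from lowest- to highest-mortality site.** With no treatment effect, the site mix alone gives:
- new protocol: (0.7×34 + 0.6×37 + 0.5×40 + 0.4×43 + 0.3×46)/2.5 = 38.8%
- standard: (0.3×34 + 0.4×37 + 0.5×40 + 0.6×43 + 0.7×46)/2.5 = 41.2%
- odds ratio: (38.8/61.2)/(41.2/58.8) = 0.905, log −0.100

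A true 1.2 would look like about 1.2 × 0.905 = 1.09. With shares of 60, 55, 50, 45, 40% the rates are 39.4% and 40.6%, the ratio is 0.951 and its log is −0.050.

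**5. False non-inferiority, hand approximation.** The standard error of the log odds ratio is about √(2/(335×0.24)) = 0.158. Pooling whenever the check misses (60.2%) and adjusting otherwise (39.8%, error 2.5%), and treating check and estimate as independent:
- 70-30: error if pooled is Φ(−1.96 + 0.100/0.158) = 9.2%; under the rule, 0.602×9.2 + 0.398×2.5 = 6.5%
- 60-40: error if pooled is Φ(−1.96 + 0.050/0.158) = 5.0%; under the rule, 0.602×5.0 + 0.398×2.5 = 4.0%

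**6. Simulation of the rule (3,000 to 8,000 trials per setting).**

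| Shares, lowest- to highest-mortality site | False non-inferiority under the planned rule |
|---|---|
| 70% to 30% | 5.4–6.3% |
| 60% to 40% | 3.6–4.1% |
| 50% at every site | 2.3–2.7% |
| 40% to 60% | 2.1% |
| 30% to 70% | 1.7–1.8% |

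With site always in the model the rate was 2.3% to 2.7%. In the 70-30 case the standard error rose from 0.158 to 0.166, a factor of 1.05.

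**7. Wider range.** These runs used 3, 5 or 8 equal sites, 672 patients and 2,000 trials per setting. The check detected site differences in 11–16% of trials at a between-site SD of 0.1 on the log-odds scale, 31–43% at 0.2, 52–68% at 0.3 and 66–85% at 0.4. With shares between 20% and 80%, the planned rule gave 5.5–9.4% when lower-risk sites used the protocol more and 2.5–4.3% when share was unrelated to risk. Equal shares gave 1.8–3.2%. Site always included gave 1.8–3.2% throughout.

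**The case against.** The strongest objection is that the protocol does not show the conditions for site confounding. Section 4.1 says participating providers follow the severity-based pathway, and no section says that sites also contribute patients managed under the other protocol. If comparators are external or historical, site is aliased with protocol and no site term can remove that confounding. This stands. It limits what the fix can achieve, but it does not justify a rule that drops site on a preliminary check.

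The number of sites, shares, alignment and significance level are also assumed. At a level of 0.20 the check would detect about 65–69% of the differences in the same setting, and the 70-30 error would fall to 4.3%. A size threshold for trivial could be left to an analysis plan. This stands as a limit on the figures. The rule itself is in the protocol, and a threshold would not make the adjustment independent of the data.

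Three stronger readings are tempting but unsupported:
- That site confounding is present. It depends on protocol use varying by site, which the document does not state.
- That the error is about 9%. In the 70-30 setting that is the rate for always pooling, which is not the planned rule.
- That the remark on type I error being deflated presents collapsing as safe. The sentence warns against ignoring nesting in either direction.

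**Conclusion.** The point holds in conditional form. The protocol fixes a rule that removes site from a non-randomised comparison on the strength of a preliminary check, and that check is weak against small to moderate site differences. In the five-site setting, false non-inferiority under the rule is about 6% or 3–4% against a nominal 2.5% when lower-mortality sites use the new protocol more. It is nominal when shares are equal and below nominal when the alignment is reversed. Always including site keeps it at about 2.5% in every alignment examined. The direction and size in this study cannot be known from the protocol. The case for change is that the alternative protects against the unfavourable pattern at very little cost, provided sites contribute patients to both groups.

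**What to change.** Delete the rule in section 4.4.1 that collapses across sites when differences are judged trivial. Pre-specify site as a fixed categorical covariate, or as a stratum, in the Hypothesis 1 model whatever the preliminary check shows, and report site heterogeneity descriptively.

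State where the patients managed under the standard protocol come from. If sites contribute to both groups, say that the adjusted effect is estimated from those sites. If comparators are external or historical, say that site is aliased with protocol and that site adjustment cannot remove this confounding.

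The cost is a few degrees of freedom (four with five sites) and a standard error up to about 5% larger in the five-site setting. About 238 deaths would be expected at the Power section's 39.7% and 31% (336×0.397 + 336×0.31), so the extra parameters are easily supported. The calculation behind 672 is unchanged.
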